recruit ethnic and racial minority groups when necessary. To be included in the study, individuals 1) were in the “core” phase of treatment or in IOP at LWNW or HBFF; 2) scored at least a four or higher on Breslau’s Short Screening Scale (Kimberling et al., 2006) for PTSD; 3) were between 18 and 70 years of age; 4) were fluent in speaking and reading English; and 5) had clearance from appropriate clinical staff. Individuals were excluded from study participation if they 1) endorsed active suicidality, hallucinations, or intense emotional lability; 2) had already participated in an MBRP group in current or past treatment; and 3) did not provide informed consent. Inclusion and exclusion criteria were assessed by the Inclusion/Exclusion Screening Tool.

Sample size estimation. For a fully-powered, cluster-randomized design, a power analysis conducted via G*Power (Faul, Erdfelder, Lang, & Buchner, 2007) using $\alpha = .05$, medium effect size across primary outcomes, mediators and moderators, a variance inflation factor of 2.55, and power level of .8 suggests a sample size of 437 participants (Donner, 1998). As a feasibility and initial efficacy trial, it is justified to recruit 10% of what is required of a fully powered clinical trial (Cocks & Torgerson, 2013; Treece & Treece, 1977); thus, we aimed to recruit 44 participants. Due to high attrition rates (56%) at a 15-week follow-up from previous research at the Phase I clinical sites (Witkiewitz, 2014), we aimed to recruit 100 participants to secure a sufficient sample size at one-month follow-up powered to analyze primary outcome data at the end of intervention implementation. We aimed for an attrition rate of 40% or less due to the short duration of the study and greater ease in contacting participants at follow-up due to most participants’ residential and active IOP status. Mediators and moderators were not included in the power analysis due to the current study being a feasibility and initial efficacy trial, and the

exploratory intention of examining mechanisms and moderators for a future, fully-powered study.

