One month after the completion of post-course assessments, participants were asked to complete a follow-up assessment battery. If participants were unable to be physically present to complete the follow-up assessment, they were offered a phone interview during which an RA administered self-report assessment measures orally.

Participants were given a \$20 gift card (not redeemable for alcohol, cigarettes, or lottery tickets) at completion of each of the first two assessments (i.e., baseline assessment, post-course assessment) and post-course focus group. A \$40 gift card was provided at completion of the one-month follow-up assessment. Total possible compensation for participation in the study was \$100.

Design and analyses. This study is an initial step in exploring the safety, feasibility, and acceptability of a novel adaptation to an evidence-based intervention. We employed a cluster-randomized, mixed methods, repeated measures design to determine feasibility, acceptability, initial efficacy, and mediators and moderators for TI-MBRP for women with co-occurring SUD and PTSD. Data from this study will inform the ecological validity and any further modifications that need to occur to the adapted protocol before conducting a larger cluster-randomized trial (Leon, Davis, & Kraemer, 2011; Moore, Carter, Nietert, & Stewart, 2011). Furthermore, determining initial efficacy and mediators and moderators will inform whether integrating

evidence-based trauma education and interventions into MBRP will reduce PTSD symptom severity and substance use indices in dually diagnosed women with PTSD-SUD more efficiently than SUD treatment alone, and inform which measures to test as mechanisms and moderators in a larger trial (Leon, Davis, & Kraemer, 2011).

Paper-and-pencil, self-report measures used at baseline, post course, and follow-up assessment points, as well as records of attendance, were double-entered into SPSS 26.0 by RAs. Prior to conduction planned quantitative analyses, data was checked for normality (skew +/- 2, kurtosis +/-2), homogeneity ($p < .05$), and accuracy using the exploratory function in SPSS (Fields, 1999). Outliers were assessed by identifying studentized residuals greater than ± 3 standard deviations. Although missing data is expected in this population, Restricted Maximum Likelihood Estimations (RMLE) allow for all participants to be included in analyses even if they present with missing data.

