Feasibility and acceptability was assessed using multiple metrics. Based on completion rates of an RCT conducted at the Phase I clinical site (Witkiewitz et al., 2014), we assessed recruitment and retention rates, with a target rate retention of 60% or better. Participant overall course satisfaction was measured by the OCSS. Treatment dropout was monitored by tracking attendance at each session and information will be gathered from clinical sites to determine whether the participant dropped out of treatment altogether or the study. This will allow assessment of any systematic bias or characteristics of TI-MBRP drop-outs vs. course completers.

To assess initial efficacy, Repeated Measures Analysis of Variance (RM ANOVA) was used to examine differences between TI-MBRP and Standard MBRP in substance use, craving, and PTSD symptoms over time. When an interaction effect was detected, an ANCOVA was used

to determine the timepoint in which two conditions differed, controlling for baseline scores (Fields, 1999). Mediators and moderators were examined using PROCESS in SPSS 26.0 to help identify factors that explain or support change in the relationships between PTSD symptom severity and craving, and PTSD symptom severity and substance use.

For Phase II qualitative data collection and analyses, ten one-hour long focus groups were audio recorded once participants completed either TI-MBRP or Standard MBRP. Women were asked eight questions to assist with the refinement of the pilot protocol (See Appendix .

Questions were as follows:

1. What was your overall experience like in this group?
2. How did this class help with understanding the relationship between substance use and trauma?
3. How did this class help with processing the impact of traumatic events on aspects of your life now?
4. How was this group different or similar from other substance use and trauma groups you have completed in the past?
5. Is there anything that you felt was missing from this program that would have enhanced your experience while taking this course?
6. What aspects of the treatment did you find helpful and/or important in your recovery process?
7. What aspects did you dislike and feel could be changed or taken out?
8. Would you recommend this group to other women who have not taken it yet?
9. How would you describe the group to other women who have not taken this group yet?

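### Clinics report who left SUD treatment, but no step carries this into the substance-use comparison, so missing outcomes rest on an untested missing-at-random (or complete-case) assumption

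*Combined protocol and SAP*

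**What the plan says.** All of this is in the Phase II part of the combined protocol and SAP.

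- **Departure information (Design and analyses, feasibility paragraph).** Attendance is tracked at each session, and "information will be gathered from clinical sites to determine whether the participant dropped out of treatment altogether or the study". The next sentence gives the purpose: "This will allow assessment of any systematic bias or characteristics of TI-MBRP drop-outs vs. course completers".
- **Missing data (Design and analyses).** The only statement on method is that "Restricted Maximum Likelihood Estimations (RMLE) allow for all participants to be included in analyses even if they present with missing data".
- **Efficacy model (Design and analyses).** Substance use, craving and PTSD symptoms are compared between arms over time by repeated measures ANOVA. If an interaction is found, an ANCOVA adjusted for baseline follows. Departure from treatment does not appear as a covariate, an outcome rule, a basis for imputation or a sensitivity analysis.
- **Follow-up (Procedures).** The last battery is due one month after the post-course assessment. For women who could not attend in person, "they were offered a phone interview during which an RA administered self-report assessment measures orally".
- **Expected loss (Sample size estimation).** The recruitment target is set "Due to high attrition rates (56%) at a 15-week follow-up from previous research at the Phase I clinical sites". The plan's own goal is looser than full retention: "We aimed for an attrition rate of 40% or less due to the short duration of the study". The feasibility paragraph repeats this as a retention target of at least 60%.

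**The concern.** Leaving SUD treatment is plausibly linked to return to use, which is one of the outcomes. The plan anticipates substantial loss and asks the clinics for the fact most relevant to it, then estimates the substance-use effect without that fact.

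REML keeps women with partial data in the analysis. It is free of bias only if, given the scores already observed, the missing values do not differ systematically from the observed ones. For a woman who left the clinic and was not reached, that means her unseen use is taken to follow the pattern of women with the same arm and earlier scores who were assessed. No analysis in the plan relaxes this.

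The results are meant to show whether adding trauma content to MBRP reduces substance use, and to shape a larger trial. A favourable or null substance-use signal could be partly a product of who was missing, and the plan as written would not reveal it.

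**Working it through.** **1. The plan's own figures.** Ten per cent of 437 is 43.7, rounded up to 44. Allowing for 56% attrition, 44 / (1 − 0.56) = 100, which reproduces the recruitment target. With 100 recruited, the 40% goal allows up to 40 missing outcomes; the historical 56% would leave 56 missing.

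**2. Formula.** Let *m* be the share of an arm with a missing outcome, *s* the share of those women who had left treatment, and *D* how much worse their substance use is, in SD, than the main model predicts from their observed data. Then:

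- error in an arm mean = *m* × *s* × *D* (the arm looks too favourable);
- error in the arm difference = the difference between the two arms in *m* × *s* × *D*.

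Only *m* has an anchor in the documents (0.40 and 0.56). The values of *s* and *D*, and any split of *m* by arm, are assumptions.

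**3. Arm level, with s = 1.**

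| Missing | D = 0.25 | D = 0.5 | D = 1 |
|---|---|---|---|
| 40% | 0.10 SD | 0.20 SD | 0.40 SD |
| 56% | 0.14 SD | 0.28 SD | 0.56 SD |

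If only half of the missing women had left treatment (*s* = 0.5), every entry halves.

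**4. Arm difference, with s = 1.**

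- Equal loss and equal *D*: 0.40 × *D* − 0.40 × *D* = 0. Only the levels are wrong.
- 30% versus 50% missing: (0.50 − 0.30) × *D* = 0.05, 0.10 and 0.20 SD for *D* = 0.25, 0.5 and 1. The error goes against the arm that kept more women.
- 35% versus 45% missing: (0.45 − 0.35) × *D* = 0.025, 0.05 and 0.10 SD.
- Equal loss of 40% but unequal effect, for example *D* = 0.5 in one arm and 0.25 in the other: 0.40 × (0.5 − 0.25) = 0.10 SD.

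**5. Check by simulation** (large samples, baseline to follow-up correlation of 0.5, assumed). With *D* = 0.5 and 40% missing, the true arm mean was about 0.20 SD, the missing-at-random likelihood estimate about 0.00, and the completer mean about −0.06. With 30% versus 50% missing, the true arm difference was about −0.09 SD and the likelihood estimate 0.00. Likelihood estimation therefore did not recover the shift, and in the single-arm example the completer mean was further from the truth.

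**6. Which assumption applies.** The missing-data statement (REML) and the efficacy paragraph (repeated measures ANOVA) are not reconciled. Classical repeated measures ANOVA drops a woman with any missing time point. If that was run, the assumption is stronger than missing at random.

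**The case against.** Several points on the other side stand, and they limit what can be claimed.

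- **A reader might infer that the departure information goes unused.** It does not: the sentence after the quoted one gives bias assessment as a purpose. What stands is that this assessment has no stated method, names drop-outs from one arm only, and is not tied to the efficacy result.
- **A reader might infer that every woman who left treatment is assumed to do as well as those who stayed.** The phone interview rules this out. A woman who left but answered contributes her own data, so the point concerns missing outcomes only.
- **A reader might infer that the treatment comparison is biased.** The documents do not show this. The error in the difference is zero when leaving and its effect are equal across arms. The idea that added trauma processing changes who leaves is possible but undocumented.
- **A reader might infer that earlier scores say almost nothing about use after leaving.** The document neither names the substance-use measure nor gives its look-back window. Residential women enter the core phase two to three weeks after detoxification, but time since detoxification is not given for IOP women, whose treatment lasts eight to 12 months. A woman missing only the follow-up also has a post-course score.

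It can also be said that this is a feasibility trial with about 44 analysable women, so one more analysis is a refinement. That argues for keeping the remedy small, and against firm conclusions from the direction of an estimate. It does not argue for omitting the check, because the trial is meant to report an initial efficacy signal.

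**Conclusion.** The point holds in a limited form. For women whose post-course or follow-up substance-use outcome is missing, the plan relies on missing at random, or on complete cases, and never tests that against departure information it intends to collect.

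If unassessed women who left treatment used more, arm levels are too favourable: by 0.20 SD with 40% missing, all of them having left, and use 0.5 SD worse, and by half that if only half had left. The arm difference is affected only if leaving or its effect differs by arm: about 0.10 SD for 30% versus 50% missing under the same assumptions. The size of the shift, the share who left and the split by arm are all assumed, so these figures show sensitivity and do not estimate the actual error. The change is worth making, but the gap is not fatal to a feasibility trial.

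**What to change.** 1. **Name one main model**: a REML mixed model using all available assessments, in place of the unreconciled pair of REML and repeated measures ANOVA.
2. **Record departure status in both arms at post-course and at follow-up**: left treatment, versus still in treatment or planned completion.
3. **Add one sensitivity analysis for substance use.** Multiply impute the missing outcomes of women who left treatment under the main model, then make them worse by a stated range, for example 0.25, 0.5 and 1 SD. If the measure is binary, count these women as using. Handle all other missing outcomes as in the main model. Multiple imputation avoids the understated variance of filling in a single value.
4. **Report it by arm beside the main result**, and describe the substance-use signal as robust only if its direction holds across the range.

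The cost is one extra analysis and one extra status item from the sites, which at present are asked only whether a woman left treatment or the study. The shift is deliberately pessimistic, and when departure differs by arm it can itself move the arm difference, so it should remain a sensitivity analysis.

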endorsed a four or higher on the BSSS and met inclusion criteria, they were offered participation in the study. Interested patients also had clearance from their primary counselors to confirm they did not meet exclusion criteria. Eligible individuals were provided with a written and oral informed consent. The PI or RA reviewed the informed consent and answer any questions or concerns that individuals had about study procedures, confidentiality, data analysis, and dissemination of results. Once written informed consent was obtained, participants were notified of the group start date within one week of signing the consent form. Participants were asked to complete a battery of paper-and-pencil assessments within one week prior to the start of the first session. After assessments were completed, cohorts of participants were randomized to receive either Standard MBRP or TI-MBRP. A non-interventionist RA used computer randomization software to assign to cohorts to either Standard MBRP or TI-MBRP. Ten TI-MBRP and Standard MBRP groups were implemented simultaneously at five sites for maximization of participants within the given timeframe over a 12-month period.

After the first Standard MBRP and TI-MBRP session, participants were provided with a CD player and CD with audio-recordings of guided meditation practices used in the intervention (i.e., body scan, breath awareness) to use daily as a part of their homework requirements. Cohorts randomized to the TI-MBRP group were given an additional CD with mindfulness practices administered only in the TI-MBRP course.

Participants completed a post-course assessment battery within one week of the completion of the eight-session course, taking place over four weeks. They had access to doctoral level psychology graduate students and to their primary counselor to discuss any distressing feelings related to the study.

One week after post-course assessments, participants were invited to participate in a focus group to discuss what was helpful about the intervention and what could be changed. Focus groups were audio-recorded, transcribed, and analyzed in NVivo Pro V12. Frequently discussed topics within focus groups were used to inform changes to the pilot protocol which will optimize interventions within TI-MBRP targeting craving, substance use and PTSD symptoms.

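### Cohorts were randomised, but the RM ANOVA and follow-up ANCOVA comparing the arms name no cohort term, so p-values can be too small

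*Combined protocol and SAP*

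**What the plan says.** Under Phase II, Procedures, "cohorts of participants were randomized to receive either Standard MBRP or TI-MBRP" once baseline assessments were complete. The same section reports that "Ten TI-MBRP and Standard MBRP groups were implemented simultaneously at five sites". Design and analyses states: "We employed a cluster-randomized, mixed methods, repeated measures design". The qualitative part of that section adds that "ten one-hour long focus groups were audio recorded once participants completed either TI-MBRP or Standard MBRP", which fits ten cohorts in total.

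For initial efficacy, Design and analyses says "Repeated Measures Analysis of Variance (RM ANOVA) was used to examine differences between TI-MBRP and Standard MBRP in substance use, craving, and PTSD symptoms". It continues: "When an interaction effect was detected, an ANCOVA was used" to find the time point at which the arms differ. Baseline score is the only covariate named.

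On missing data, the same section says that "Restricted Maximum Likelihood Estimations (RMLE) allow for all participants to be included in analyses even if they present with missing data". No section names a cohort or site effect, a random effect, an ICC for this trial, a cluster-robust standard error or a cohort-level test. Clustering enters the numbers once, in Sample size estimation, for the future full trial: "a variance inflation factor of 2.55, and power level of .8 suggests a sample size of 437 participants".

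**The concern.** When cohorts are randomised, evidence about the arm effect comes from differences between cohorts. With ten cohorts in two arms, 10 − 2 = 8 df are available. The analyses as written take their error from women. With 60 women at three time points, the RM ANOVA interaction has (60 − 2) × 2 = 116 error df, and the ANCOVA has 60 − 3 = 57.

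The difference matters only if outcomes within a cohort are correlated in a way the test picks up. That is plausible here: women took the course together, and delivery was by the PI and three research assistants, so a cohort also shared its facilitator. Such influences begin after baseline, and this is the pattern that distorts a condition-by-time test.

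A significant interaction could then reflect a few unusual groups rather than the treatment. It would trigger the ANCOVA and be carried forward as a sign of efficacy, since Design and analyses uses initial efficacy to inform whether the integration works and to prepare a larger cluster-randomised trial.

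The point covers the arm comparisons only, not the PROCESS models or the feasibility outcomes.

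**Working it through.** **1. The plan's own figures.** 10% of 437 is 43.7, rounded to 44, and 100 × (1 − 0.56) = 44; both reproduce. The 437 does not follow from its stated inputs: a two-group, two-sided 5% test with 80% power and an assumed d = 0.5 needs 128, and 128 × 2.55 = 326.4. That is a separate matter. Only the factor 2.55 is used below.

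**2. Inputs.** From the documents: cohort as the randomised unit; ten cohorts (likelier reading); 100 to recruit; attrition target of at most 40%; α = 0.05. Cohort sizes follow: 100/10 = 10, 60/10 = 6, and 44/10 ≈ 4. Assumed, because not given: ICC, within-woman correlation 0.5, equal cohort sizes, complete data, and when the cohort effect arises.

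**3. ICC range.** From VIF = 1 + (m − 1) × ICC:
- cohorts of 10: (2.55 − 1)/(10 − 1) = 0.172, an upper scenario, because it moves the full-trial factor onto this trial's cohort size;
- 437 women in ten clusters of 43.7: (2.55 − 1)/(43.7 − 1) = 0.036.

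**4. Approximate check.** If the variance is understated by a factor D = 1 + (m − 1) × ICC, the true type I error is about 2 × [1 − Φ(1.96/√D)]. At m = 6 and ICC 0.05, D = 1.25 and the error is 0.080. At D = 2.55 it is 0.22.

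**5. Simulation.** Ten cohorts (5 v 5), three time points, no treatment effect, sphericity-assumed RM ANOVA, 5,000 trials per cell. Rejection rate of the nominal 5% interaction test at m = 10 / 6 / 4:

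| Cohort effect | ICC 0.036 | ICC 0.05 | ICC 0.172 |
|---|---|---|---|
| Arises after baseline | 0.088 / 0.069 / 0.059 | 0.108 / 0.077 / 0.065 | 0.208 / 0.153 / 0.110 |
| Half stable, half post-baseline | 0.069 / 0.057 / 0.052 | 0.070 / 0.061 / 0.060 | 0.140 / 0.099 / 0.074 |
| Stable at all times | 0.048 / 0.045 / 0.056 | 0.046 / 0.048 / 0.045 | 0.049 / 0.047 / 0.049 |

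A stable cohort effect cancels from the interaction, as the last row shows. A separate simulation with 20,000 trials per setting gave 0.078 (m = 6) and 0.099 (m = 10) at ICC 0.05, and 0.161 and 0.231 at ICC 0.172. The largest cell ranged from 0.21 to about 0.24 across simulations. That exceeds Monte Carlo error (about 0.006) and reflects whether the cohort variance is added to the total or taken out of it.

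The post-course ANCOVA taken alone, at ICC 0.172, rejected in 0.255 / 0.175 / 0.130 (post-baseline), 0.197 / 0.132 / 0.095 (half) and 0.098 / 0.080 / 0.064 (stable).

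**6. If there were twenty cohorts.** With a post-baseline effect, the interaction test rejected in 0.072 (m = 5) and 0.060 (m = 3) at ICC 0.05, and in 0.136 and 0.092 at ICC 0.172.

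**7. Cohort-level test.** A t-test on baseline-adjusted cohort means rejected in 0.044 to 0.055 of trials in every ten-cohort cell (8 df). Paired by site with 4 df it rejected in 0.042 to 0.059; this assumes one cohort of each arm per site, which the documents do not state.

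**8. Cost in power.** With baseline correlation 0.5 the residual variance is 1 − 0.5² = 0.75. At ICC 0.05 and m = 6:
- cohort respected: SE = √[2 × (0.05 + 0.95 × 0.75/6)/5] = 0.260;
- cohort ignored: SE = √[2 × (0.05 + 0.95 × 0.75)/(5 × 6)] = 0.225.

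By noncentral t, the difference detectable with 80% power is 0.64 SD nominally (cohort ignored), 0.83 SD with 8 df (critical t 2.31) and 0.98 SD with 4 df (critical t 2.78). The last figure assumes that site adjustment removes no variance.

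**The case against.** The strongest reply is that this reads too much into a short document. Classical RM ANOVA cannot keep women with missing visits, yet the plan says REML does, so a mixed model may have been fitted and the simulated analysis may not be the one used. This stands as a caution about size. It does not answer the point: REML is offered only for missing data, and a model with woman-level effects alone would still ignore the cohort.

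Second, the size rests on assumptions. The highest rates need ICC 0.172, ten women per cohort with no loss, and an entirely post-baseline effect. At ICC 0.036 to 0.05 with 4 to 6 women per cohort the interaction error is only 0.06 to 0.08. This is fair, and the conclusion is worded conditionally for that reason.

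Third, the ANCOVA runs only after a significant interaction, so its stand-alone rates overstate the two-step error. Under a post-baseline cohort effect, a significant interaction together with at least one significant ANCOVA occurred in 0.043 to 0.059 of simulated trials at ICC 0.036 to 0.05 with 4 to 6 women, in 0.07 to 0.09 with 10 women, and in 0.10 to 0.23 at ICC 0.172. Gating therefore softens the problem at the low end, but it does nothing for the interaction test itself.

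Fourth, the text on the number of groups could mean ten per arm. The inflation would be smaller but still present, and the cohort-level test would have 18 df.

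Finally, this is a feasibility trial with no stated go/no-go rule tied to a p-value. That limits the harm. It does not justify the wrong unit of inference for a comparison the plan uses to judge initial efficacy.

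**Conclusion.** The concern holds. Randomisation by cohort and the named arm comparisons do not match, and nothing else in the document supplies the missing cohort term. Confidence in that mismatch is high.

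The size is conditional. With ten cohorts and a shared effect arising after baseline, the interaction test's true level is about 0.06 to 0.11 at ICC 0.036 to 0.05, and 0.11 to 0.21 (up to about 0.24 depending on how the variance is set up) at ICC 0.172. With a mixed pattern it is 0.05 to 0.07 and 0.07 to 0.14 respectively. With a fully stable cohort effect it is about 0.05, and only the ANCOVA is inflated. The ICC, the within-woman correlation and the timing of the effect are assumptions; ten cohorts is the likelier reading of the text.

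This should be fixed before the arm comparisons are used as evidence of efficacy. It does not affect the feasibility findings.

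**What to change.** Name the cohort as the unit of inference for every arm comparison, and state the number of cohorts per arm and per site.

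- **Simplest choice:** a t-test on baseline-adjusted cohort means at each post-baseline time point, with 8 df and no site term. If site is to be a fixed effect, about 4 df remain. Settle on one option before the reanalysis is run and use it for all outcomes. Because the plan describes the analysis as already done, report the result as a reanalysis.
- **Alternative:** a linear mixed model fitted by REML with condition, time, condition-by-time, baseline adjustment for the post-baseline contrasts, repeated measures within woman, one random cohort effect on the post-baseline scores, and Satterthwaite or Kenward-Roger df. Fall back to the cohort-mean test if the cohort variance is estimated at zero.
- **Reporting:** give each outcome's ICC with its interval, for use in planning the larger trial. Label the PROCESS results exploratory and not adjusted for clustering.

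If a cohort effect was in fact fitted, it is enough to say so and give the model and df.

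The cost is revised SAP wording and a short reanalysis of existing data in software already used. p-values will be larger and power lower, as the detectable differences in step 8 of the working show. The ICC will also be imprecise: an estimate of 0.05 from ten cohorts of six has a 95% interval of about −0.08 to 0.40 (F method, 8 and 50 df).

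### The test that decides initial efficacy works on unadjusted change; baseline adjustment enters only in an ANCOVA run after an interaction has been found

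*Combined protocol and SAP*

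**What the plan says.** In the combined protocol and SAP, Phase II, Procedures, the baseline battery comes first: "Participants were asked to complete a battery of paper-and-pencil assessments within one week prior to the start of the first session". Cohorts are randomised only after those assessments are complete. Design and analyses names three assessment points: baseline, post-course and follow-up.

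The same section gives the efficacy analysis: "Repeated Measures Analysis of Variance (RM ANOVA) was used to examine differences between TI-MBRP and Standard MBRP in substance use, craving, and PTSD symptoms", with time as the repeated factor. If that analysis shows an interaction, an ANCOVA adjusting for the baseline score is then used to find the visit at which the arms differ. The section also says that restricted maximum likelihood keeps participants with missing data in the analysis.

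Sample size estimation gives the planning figures: "medium effect size across primary outcomes, mediators and moderators", then "a variance inflation factor of 2.55, and power level of .8 suggests a sample size of 437 participants", then 10% of that ("thus, we aimed to recruit 44 participants"), and finally "we aimed to recruit 100 participants to secure a sufficient sample size at one-month follow-up".

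**The concern.** Because baseline precedes randomisation, the arms can differ there only by chance. A baseline score is then most useful as a covariate that removes noise from the later scores. If it is one level of the time factor, the arm-by-time interaction compares unadjusted changes, which carry the full noise of the baseline score and any chance gap between arms. With ten groups as the randomised units, such gaps are likely.

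The plan's baseline-adjusted comparison is reached only through the less precise test. With 44 to 60 women expected at follow-up, precision is scarce, and the results are meant to inform a larger trial.

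**Working it through.** **Inputs from the documents.** Alpha .05 (two-sided assumed). Recruitment 100. Attrition of 56% leaves 100 × .44 = 44; the 40% target leaves 100 × .60 = 60. Three visits. Variance inflation factor (VIF) 2.55.

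**Assumptions, because the documents give no figure.** Medium is taken as d = .5 in SD units. The correlation ρ is equal between all visits, .5 with a range of .3 to .8. Arms are equal in size. Four time courses are used for the effect at (post-course, one month).

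**The plan's own figures.** No power is stated for the RM ANOVA. The 10% step reproduces: 437 × .10 = 43.7, so 44. The 437 does not reproduce under the common reading: d = .5 at 80% power needs 128 by the t test, and 128 × 2.55 = 326, while 437/2.55 = 171.4. The G*Power test is not named and medium is not quantified, so this is a failure to reproduce, not a proven error. Nothing below depends on it.

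**Noise at one visit, ρ = .5.** Unadjusted change: 2(1 − .5) = 1.00. Baseline-adjusted score: 1 − .5² = .75.

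**RM ANOVA interaction.** Noncentrality λ = (N/4) × Σ(δt − mean δ)²/(1 − ρ), with 2 and 2(N − 2) df. For a sustained effect δ = (0, .5, .5) and the sum of squares is 1/6.
- N = 44: 11 × .1667/.5 = 3.67, power 37.3%.
- N = 60: 15 × .1667/.5 = 5.00, power 49.3%.

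**Baseline-adjusted joint test of both post-baseline visits.** λ = (N/4) × δ'Σ⁻¹δ, with 2 and N − 4 df. Σ has diagonal 1 − ρ² = .75 and off-diagonal ρ − ρ² = .25. For a sustained effect δ'Σ⁻¹δ = .50.
- N = 44: 11 × .50 = 5.50, power 51.2%.
- N = 60: 15 × .50 = 7.50, power 66.3%.

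**Other time courses, ρ = .5, no clustering (power, RM ANOVA then joint adjusted test).**

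| Effect at post-course, one month | N = 44 | N = 60 |
|---|---|---|
| .5, .5 (sustained) | 37.3%, 51.2% | 49.3%, 66.3% |
| .25, .5 (growing) or .5, .25 (fading) | 28.8%, 37.0% | 38.3%, 49.4% |
| .5, 0 (vanishing) | 37.3%, 39.9% | 49.3%, 53.1% |

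**Range over ρ = .3, .5, .7, .8 at N = 60.**
- RM ANOVA, sustained or vanishing (same sum of squares): 36.7, 49.3, 72.4, 88.8%.
- Joint test, sustained: 61.0, 66.3, 81.0, 92.2%.
- Joint test, vanishing: 42.7, 53.1, 73.9, 89.1%.

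At N = 44, ρ = .8 and a vanishing effect, the two are level (76.3% and 76.2%).

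**Clustering.** Dividing λ by 2.55 (sustained, ρ = .5) gives 16.8% v 22.6% at N = 44 and 21.7% v 30.1% at N = 60. Denominator df are unchanged here; df based on ten cohorts would lower both.

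**Is the gain from adjustment?** Both tests above have 2 df, so no visit has been singled out. At post-course alone, on 1 df and with a .5 effect, unadjusted change gives 36.7% (N = 44) and 47.8% (N = 60), against 46.4% and 59.4% for ANCOVA.

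**Single contrasts can lose, ρ = .5.**
- Post-course ANCOVA, λ = (N/4)d²/(1 − ρ²), growing effect, N = 60: 15 × .0625/.75 = 1.25, power 19.6% v 38.3% for the RM ANOVA.
- Adjusted mean of both visits, λ = (N/4)(mean d)²/[(1 + ρ)/2 − ρ²], effect fading from .5 to .1, N = 44: 11 × .09/.5 = 1.98, power 27.9% v 31.9%.

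**The two-step route.** In simulation (N = 60, ρ = .5, sustained, no clustering), the interaction and then the post-course ANCOVA were both significant in 39.2% of runs; the ANCOVA run directly was significant in 58.6%.

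**The case against.** **The plan does adjust for baseline.** True. A reader might infer that baseline is never a covariate, and the documents do not support that. The point is narrower: the adjusted analysis depends on a prior test that does not adjust.

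**The model is inferred.** The levels of the time factor are not listed, and the restricted maximum likelihood sentence fits poorly with a classical RM ANOVA. Three levels including baseline is the natural reading of an analysis over time that is followed by an ANCOVA on baseline, but it remains a reading.

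**The loss is not a fixed number.** A reader might infer a set loss of 9 to 10 points (against an adjusted post-course test) or more than 25 points (against an adjusted mean of both visits). Those figures hold only at ρ = .5 with a sustained effect and no clustering. At ρ = .8 the post-course figure is about zero, and with the VIF at ρ = .5 it is about 5 to 6 points. About 9 of the 25.7 points for the adjusted mean at N = 44 come from using one contrast, since its unadjusted version already reaches 46.5%.

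**Post-course is not shown to be the safer lead.** The sample-size text says "powered to analyze primary outcome data at the end of intervention implementation", but the same sentence also refers to one-month follow-up. It does not settle a single deciding visit, and the growing-effect case shows the risk.

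**Clustering matters more for validity.** If a VIF of 2.55 is real and ignored, a nominal 5% test rejects about 22% of the time under no effect (normal approximation: 1.96/√2.55 = 1.23). The unclustered powers therefore only compare the two tests, and any replacement needs a cohort term.

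**This is a feasibility and initial efficacy trial.** That limits the consequence. It does not remove it, because the efficacy results are to inform the larger trial.

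**Conclusion.** The point holds as a matter of efficiency. As most naturally read, the deciding test leaves a pre-randomisation baseline score unused as a covariate. At d = .5, ρ = .5 and no clustering, a like-for-like adjusted 2-df test gains about 14 points at N = 44 and 17 at N = 60 if the effect is sustained, about 8 and 11 if it grows or fades by half, and about 3 to 4 if it vanishes. With the plan's VIF the sustained gains are about 6 and 8 points. In the unclustered cases above the adjusted joint test matches or beats the RM ANOVA, with gains approaching zero at ρ = .8 when the effect vanishes. All sizes rest on an assumed effect, correlation and time course.

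A reader might go further and call the RM ANOVA biased for lack of adjustment. The documents do not support that: baseline precedes randomisation, so the cost is lost precision plus whatever chance imbalance the realised sample has. The change is advisable and does not bear on whether the trial is sound as a feasibility study.

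**What to change.** In Design and analyses, make the efficacy analysis for each outcome a baseline-adjusted repeated-measures model fitted by restricted maximum likelihood, which the section already mentions:

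- Outcomes: the post-course and one-month scores.
- Covariates: that outcome's own baseline score and baseline-by-time.
- Effects: arm, time, arm-by-time, and a random effect for cohort, the randomised unit.
- Test: arm jointly at the two post-baseline visits (2 df).
- Reporting: both visit-specific adjusted differences with confidence intervals, whether or not an interaction is found.

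Keep the RM ANOVA as a description of trajectories. Let a single post-course contrast or a mean of both visits lead only if the expected time course justifies it in advance.

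The cost is revised SAP wording and a modest re-analysis of data already collected, with no new participants or visits. The plan is written in the past tense, so the re-analysis must be labelled as a change made after data collection, with the RM ANOVA result shown beside it so that the choice does not look driven by results.
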